#### **Exclusion Criteria**

1. Known or suspected hypersensitivity to POM, LEN, thalidomide, DEX or to any of the excipients

Sponsor: MorphoSys AG

Confidential

2. Subject who are refractory (defined as progression during or within 60 days after their last dose of POM) or intolerant to POM

During the treatment with POM, the investigators need to follow the corresponding Pregnancy prevention risk minimization plans (see Appendix 18.8.2).

# 8.3 Definition of Woman of Childbearing Potential

This protocol defines a female of childbearing potential as a sexually mature woman who:

- has not undergone a hysterectomy or bilateral oophorectomy or
- has not been naturally postmenopausal (amenorrhea following cancer therapy does not rule out childbearing potential) for at least 24 consecutive months (i.e., has had menses at any time in the preceding 24 consecutive months).

# 8.4 **Procedures for Enrollment**

A full written informed consent must be available before the start of screening activities. In addition, for subjects who could potentially be assigned to the MOR03087 + LEN + DEX or MOR03087 + POM + DEX combination therapy parts, a pregnancy prevention information leaflet must also be available before assignment to these parts (see Appendix 18.8).

Enrolment will be performed at baseline after all inclusion and exclusion criteria have been checked and the subject is found to be eligible. Enrolment will be performed by means of an interactive web response system (IWRS) connected to the electronic data capture (EDC) system. The investigator will be informed about the enrolment via an e-mail or FAX.

Part A dose levels 1-7 will be tested sequentially, and only one dose level will be open for enrolment at any time. Starting with Part A dose level 8, Parts B and C will open in parallel (at dose level 6 [6b and 6c]). Following completion of dose level 7c (8.0 mg/kg MOR03087 + DEX) (and dose level 7b if the DMC recommends to open this cohort), Cohorts 7d and 7e may open in parallel with dose levels 8b (if the DMC recommends to open this cohort) and 8c. New cohorts will not start before the DMC returns a positive recommendation based on safety read-outs from prior cohorts as laid down in the DMC Charter.

# 8.5 Dose Limiting Toxicities

Adverse events will be graded according to NCI CTCAE, version 4.0, with a DLT being defined as an AE assessed as having a suspected or unknown relationship to the study drug (MOR03087, POM, or LEN) and meeting one of the following criteria:

- Non-hematologic DLT:
  - o Liver

Any grade 3 AST/ALT that does not resolve to grade 1 within 14 days or any grade 4 elevation in liver function tests (AST/ALT)

- Gastrointestinal
  - $\geq$  Grade 3 vomiting or nausea despite the use of standard antiemetics

Sponsor: MorphoSys AG

- $\geq$  Grade 3 diarrhea or constipation despite the use of optimal treatment
- All other events
  - ≥ Grade 3 (excluding hypersensitivity reactions and fatigue)
- Hematologic DLT:
  - Grade 4 thrombocytopenia that requires more than one platelet transfusion and does not resolve to grade 2 or less within 14 days
  - Grade 4 neutropenia that does not resolve to grade 2 or less within 14 days
  - Or any other grade 4 hematologic toxicities that do not resolve to grade 2 or less within 14 days and that are considered clinically relevant by the investigator
- Any AE that delays treatment with study drug for more than 14 days

In addition, any event will only qualify as a DLT if a worsening of the event from baseline of at least 2 CTCAE Grades occurs.

The DLTs for the POM combination cohorts are specified as above except for the hematological DLTs which are as follows:

- Hematologic DLT:
  - Grade 4 neutropenia for > 7 days
  - Febrile neutropenia (ANC <1000/mm³ with a single temperature of >38.3°C or a sustained temperature of  $\geq$  38°C for more than 1 hour)
  - o Thrombocytopenia
    - Platelet count  $< 25,000/\mu$ L that requires more than one platelet transfusion or
    - Platelet count  $\ge 25,000/\mu L$  to  $< 50,000/\mu L$  with significant bleeding (defined as need for hospitalization and/or platelet transfusion)
  - Or any other grade 4 hematologic toxicities that do not resolve to grade 2 or less within 14 days and that are considered clinically relevant by the investigator

The DLTs for the LEN combination cohorts are specified as above except for the hematological DLTs which are as follows:

- Hematologic DLT:
  - Grade 4 neutropenia for > 7 days
  - Febrile neutropenia (ANC <1000/mm³ with a single temperature of >38.3 °C or a sustained temperature of  $\geq$  38 °C for more than 1 hour)
  - o Thrombocytopenia
    - Platelet count  $< 30,000/\mu$ L that requires more than one platelet transfusion or
    - Platelet count  $\ge$  30,000/µL to < 50,000/µL with significant bleeding (defined as need for hospitalization and/or platelet transfusion)
  - Or any other grade 4 hematologic toxicities that do not resolve to grade 2 or less within 14 days and that are considered clinically relevant by the investigator

The DLT period covers Day 1 of cycle 1 (starting with first study drug administration) until Day 29 (before start of the second cycle). Granulocyte-colony stimulating factor (GCSF) therapy is prohibited during this time.

Laboratory DLTs will be reported as AEs.

Sponsor: MorphoSys AG

Confidential

Subjects experiencing DLTs in the study should not receive further study drug.

If upon treatment with POM or LEN, subjects present with protocol-defined DLTs or toxicities or conditions described in the corresponding Section 9.1.4, treatment must be modified or interrupted accordingly.

If upon treatment with DEX, subjects present with protocol-defined toxicities or conditions described in the corresponding SmPC, treatment must be modified or interrupted accordingly.

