	 Non-hematologic DLT: Liver Any grade 3 AST/ALT that does not resolve to grade 1 within 14 days or any grade 4 elevation in liver function tests (AST/ALT) Gastrointestinal Grade 3 vomiting or nausea despite the use of standard antiemetics Grade 3 diarrhea or constipation despite the use of optimal treatment All other events Grade 3 (excluding hypersensitivity reactions and fatigue) Hematologic DLT: Grade 4 thrombocytopenia that requires more than one platelet transfusion and does not resolve to grade 2 or less within 14 days Grade 4 neutropenia that does not resolve to grade 2 or less within 14 days or any other grade 4 hematologic toxicities that do not resolve to grade 2 or less within 14 days or any other grade 4 hematologic toxicities that do not resolve to grade 2 or less within 14 days or any other grade 4 hematologic toxicities that do not resolve to grade 2 or less within 14 days or any other grade 4 hematologic toxicities that do not resolve to grade 2 or less within 14 days or any other grade 4 hematologic toxicities that are considered clinically relevant by the investigator Any AE that delays treatment with study drug for more than 14 days In addition, any event will only qualify as a DLT if a worsening of the event from baseline of at least 2 CTCAE Grades occurs. The DLTs for the POM combination cohorts are specified as above except for the hematological DLTs which are as follows: Hematologic DLT: Grade 4 neutropenia for > 7 days

	Parts A, B, C: MOR03087
Pharmacokinetics	Concentration-time profiles and pharmacokinetic parameters of MOR03087 +/- LEN or POM will be assessed from samples collected on the following schedules (if not otherwise specified, a deviation of 5 minutes from the planned collection time point will be acceptable):
Subject-Reported Outcomes/Quality of Life	Quality of life will be evaluated using the QLQ-30 and the QLQ-MY20, an instrument for use in subjects with MM.
	Subjects experiencing DLTs should not receive further study drug. A pharmacokinetic interim analysis may be performed at any time during dose escalation if unexpected MOR03087 serum concentration results are observed.
	The DLT period covers Day 1 of cycle 1 (starting with first study drug administration) until Day 29 (before start of the second cycle).

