Following completion of Parts D and E (dose escalation of MOR03087 in combination with POM+DEX and LEN+DEX), the MTD and/or recommended dose in each part will be confirmed in a minimum of 6 subjects.

All cohorts:

After the first administration of study drug, the subjects will remain at the site until the end of Day 2 for safety monitoring. The subjects will not stay overnight at the site for subsequent administrations.

Based on the individual risk/benefit ratio, subjects who have an ongoing response of at least stable disease (SD) may continue treatment with the assigned study regimen until disease progression or until a maximum of 3 years after first treatment. In case subjects present with progressive disease or with no better status than SD after four treatment cycles starting with Cycle 1 Day 1, the investigator may add a low weekly dose of DEX to the regimen at his/her discretion, provided DEX is not already part of the treatment regimen.

At least 3 subjects meeting all inclusion and none of the exclusion criteria, as determined at the screening visit (see Sections 8.1 and 8.2) will be enrolled into each cohort.

Enrolment into a cohort at the next higher dose level will be based on the data generated from the previous dose level and guided by clinical review until

- the maximum planned dose has been reached, or
- the review of the safety data indicates a need to either expand the current dose level cohort to include 6 subjects or stop the dose escalation or the study, or
- the review of Part B dose level 6b and Part C dose level 6c, including available safety information from Part A dose level 8, indicates that only some of the planned weekly MOR03087 monotherapy dose escalation cohorts should be tested.

The DMC safety review will take place after the third subject enrolled into a cohort has undergone minimum safety evaluations (as defined for the "DLT Evaluable Population" in Section 15.1). The safety assessment will take into account AEs reported from Day 1 after the start of the first infusion through Day 29 before the start of the second cycle. The next cohort will only be started after the positive outcome of the safety assessment.

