Cohort expansion up to 6 subjects will be allowed if a dose limiting toxicity (DLT) (as defined in Section 8.5) is observed in 1 of 3 subjects. If 2 or 3 subjects experience a DLT in cohorts 6b or 6c, the study sponsor may decide to test a lower dose. If 2 or 3 subjects of the 3 subjects in any of the other cohorts experience DLT, then the previous cohort should be expanded to 6 subjects.

A pharmacokinetic interim analysis may be performed at any time during dose escalation if unexpected MOR03087 serum concentration results are observed. The rationale for performing the pharmacokinetic interim analysis is to verify whether the derived pharmacokinetic parameters from this interim analysis (e.g., C_{max} , AUC, terminal elimination half-life, etc.) are still within the expected range. If there are major deviations from the expected values, it may be considered necessary to investigate a further dosing regimen or to expand the dose escalation including further cohorts via a substantial amendment to the protocol.

After study drug discontinuation due to reason other than disease progression, all subjects will return for a follow-up visit 1 and follow-up visit 2. Further follow-up visits will be conducted at 4-week intervals until the subject is progressive, begins subsequent anti-myeloma therapy, or dies.

All subjects will be followed up for a maximum of 3 years after first administration of study drug.

Study visits will be conducted according to the Schedules of Assessments provided in Table 1 (for subjects receiving bi-weekly MOR03087 treatment) and Table 2 (for subjects receiving weekly/bi-weekly MOR03087 treatment).

]	Freatme	nt (Tx) C	Cycle 1 (I	Days 1-28	8)	Тх	Cycle 2	(Days 29	-56)	Tx Cycles 3+	Follow-up	Follow-up Visit 2	EOS Visit ²
Evaluation or Procedure	Screening (≤ 4 weeks before Day 1)	D1	D2	D4	D8 ± 1 day	D15 ±1 day	D22 ±1 day	D29 C2D1 ±1 day	D36 C2D8 ± 1 day	D43 C2D15 ± 1 day	D50 C2D22 ± 1 day	Visit: repeated bi- weekly (± 2 days)	Visit 1 (4 weeks ± 2 days after last dose)	(4 weeks ± 2 days after Follow-up Visit 1) ¹	
Informed consent	X														
Medical history ³	X														
Demography	X														
Inclusion/exclusion criteria	X	X ⁴													
Karnofsky performance status	X	X ⁴								X4		X^5	Х	Х	Х
Premedication		X ⁶		X ⁶		X ⁶		X ⁶		X ⁶		X ⁶			
Study drug administration (2-hour infusion)		Х		X		Х		X		X		Х			
Laboratory															
"Emergency laboratory"7		X ⁸		X8		X ⁸		X8		X8		X			

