# 8.6 Other Reasons for Treatment Postponement

Study drug administration may be delayed for medical or other reasons (e.g., social reasons, weather circumstances). In case of a delay in study drug administration, the treatment should be restarted as early as possible. Should treatment be delayed for more than 14 days after the missed dose, then the treatment should be permanently discontinued. The subject should continue with the first follow-up visit in the study.

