- Severe: Incapacitating (causes inability to perform usual activity or work)

The toxicity grade of AEs will be graded according to the NCI CTCAE (version 4.0 of May 28, 2009) using the following definitions:

- Grade 1: Mild; asymptomatic or mild symptoms; clinical or diagnostic observations only; intervention not indicated.
- Grade 2: Moderate; minimal, local or non-invasive intervention indicated; limiting age-appropriate instrumental activities of daily living (refers to

preparing meals, shopping for groceries or clothes, using the telephone, managing money, etc.).

- Grade 3: Severe or medically significant but not immediately life-threatening; hospitalization or prolongation of hospitalization indicated; disabling; limiting self-care activities of daily living.
- Grade 4: Life-threatening consequences; urgent intervention indicated.
- Grade 5: Death related to AE.

The causal relationship of all AEs to IMP intake will be judged as either suspected or not suspected. If no relationship has been provided by the investigator, the event will be considered as related to study drug and notified to authorities according to regulatory reporting requirements.

In addition to the investigator's own description of the AEs, each AE will be encoded by the sponsor (or its delegate) according to the current version of the Medical Dictionary for Regulatory Activities (MedDRA).

All non-serious AEs must be followed up for a final outcome until resolution or until the EOS visit. An outcome of "unknown" is not considered to be an acceptable final outcome. An outcome of "not yet resolved" is an acceptable final outcome for non-serious AEs at the end of a subject's participation in a study. SAEs must be followed up for a final outcome until resolution or, if resolution becomes unlikely, until stabilization or death. This includes obtaining information on recovery and any sequelae and, in case of a fatal outcome, the cause of death. For SAEs which are due to progression of MM, follow-up only until the end of subject's participation in the study is acceptable.

will report all reportable events to all competent authorities (including the European Medicines Agency [EMA]), IECs or Institutional/Independent Review Boards (IRBs), and investigators as required by local regulations and Premier Research standard operating procedures (SOPs).

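### The hypersensitivity exemption in the DLT definition has no upper grade, so a fatal Cycle 1 reaction classed as hypersensitivity is, as written, not a DLT

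*Protocol*

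**What the plan says.** Protocol 8.5 lists liver, gastrointestinal, catch-all and hematologic criteria, plus one on treatment delay. The catch-all covers remaining non-hematologic events from grade 3 upwards, with the exemption "Grade 3 (excluding hypersensitivity reactions and fatigue". The synopsis carries the same clause: "All other events Grade 3 (excluding hypersensitivity reactions and fatigue". The liver criterion is built differently. A grade 3 AST/ALT rise that resolves in time is spared, but the text adds "or any grade 4 elevation in liver function tests (AST/ALT". The delay criterion reads "Any AE that delays treatment with study drug for more than 14 days". The POM and LEN versions replace only the hematologic criteria.

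The grading scale in Protocol 12.1 ends at "Grade 5: Death related to AE". Protocol 9.1.1 and 9.1.3 require a subject with a grade 3 or 4 infusion reaction to stop study drug for good. Protocol 8.6 says of postponed doses: "Should treatment be delayed for more than 14 days after the missed dose, then the treatment should be permanently discontinued".

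The definition drives the escalation. Protocol 7.1 allows expansion to 6 when a DLT ("as defined in Section 8.5) is observed in 1 of 3 subjects"). SAP 10.1 places the MTD one level below the dose at which 2 of 3 or 2 of 6 subjects have a DLT. Protocol 15.1 and SAP 6 exclude from the DLT Evaluable Population anyone who stops treatment in Cycle 1 for a reason other than a DLT. Protocol 8.7.1 and SAP 8.2 replace non-evaluable subjects during escalation, but not withdrawals due to a DLT.

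**The concern.** An exemption for hypersensitivity in an antibody trial is an understandable choice: such reactions may not depend on dose. One with no ceiling goes further, because it takes in life-threatening and fatal reactions. The liver criterion in the same list shows that the authors knew how to cap an exemption.

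The MTD is part of a primary endpoint in a first-in-human study. If the definition leaves out a drug-related death, the pre-specified count can show a clean cohort. The replacement rule can then remove the subject from the denominator as well. Any correction would rest on someone deciding to depart from the written rule.

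**Working it through.** **1. Criteria read against the event.** Take a drug-related hypersensitivity reaction in Cycle 1.

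| Criterion in Protocol 8.5 | Fatal (grade 5) | Grade 4 |
|---|---|---|
| Liver (AST/ALT) | not met | not met |
| Gastrointestinal | not met | not met |
| Catch-all, grade 3 or higher | exempt | exempt |
| Hematologic (general, POM, LEN) | not met | not met |
| Delay over 14 days | not met: a death delays no treatment | met if dosing is actually delayed that long; unclear if drug is stopped for good |

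So a fatal reaction meets no criterion. A grade 4 reaction with a mandated stop counts only if a permanent stop is read as a delay. Protocol 8.6 links the two, but as successive steps, and 8.5 does not say that a stop is a delay.

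**2. Effect on the count.** No assumed rate is needed.
- One fatal reaction among the first 3, before the minimum doses: the subject is excluded and replaced. If the others have no DLT, the cohort reads 0/3 and the next dose may open. Counted, it reads 1/3 and allows expansion to 6.
- One ordinary DLT among the first 3, then one fatal reaction in the expansion: after replacement it reads 1/6. Counted, it reads 2/6, which under SAP 10.1 puts the MTD at the level below.
- If the death follows the minimum doses and the subject is kept as evaluable, the event still adds nothing to the numerator.

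**3. Effect on one cohort's stop probability.** The plan gives no figure on this point. Its only sample-size figures (Protocol 15.9, 9 subjects) reproduce: 1 − 0.83^9 = 0.813 and 1 − 0.77^9 = 0.905, against the stated 81% and 90%. The point does not depend on them.

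With DLT rate r, a cohort passes with 0/3, or with 1/3 followed by 0/3. Therefore

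S(r) = 1 − [(1 − r)^3 + 3r(1 − r)^5].

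Assumptions, none from the documents: other DLTs occur at q = 10%; uncounted reactions occur at p = 0.5%, 1% or 2%; the two do not overlap; every subject with an uncounted reaction is replaced. As written, the rate among evaluable subjects is q/(1 − p). If the reactions count, it is q + p.

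For p = 1%:
- As written: r = 0.10/0.99 = 0.1010, S = 1 − (0.72655 + 0.17793) = 0.0955.
- Counted: r = 0.11, S = 1 − (0.70497 + 0.18427) = 0.1108.

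| p | S as written | S if counted |
|---|---|---|
| 0.5% | 9.5% | 10.2% |
| 1% | 9.6% | 11.1% |
| 2% | 9.7% | 12.9% |

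**The case against.** The strongest reply is that the raw DLT count does not decide alone. No cohort opens without a positive DMC recommendation. Protocol 7.1 lets enrolment change course when "the review of the safety data indicates a need to either expand the current dose level cohort to include 6 subjects", and the same clause allows escalation or the study to be stopped. In SAP 10.1 a sponsor or DMC decision, where recorded, overrides the investigator's DLT entry. The recommended dose rests on all safety data and may lie below the MTD. For a death to go uncounted, the sponsor and DMC would have to leave it unflagged. All of this stands and limits the practical effect. But these routes are discretionary, set no grade threshold for hypersensitivity, and leave the written definition as it is.

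The exempt class is also narrower than it may look. A reader might infer that every severe infusion reaction or cytokine release escapes. The documents do not support that: Protocol 12.1 lists infusion reactions, cytokine release syndrome and allergic reactions separately, so a grade 3 or higher event classed as one of the first two, and not as hypersensitivity, remains a DLT. Because hypersensitivity is not defined, the result depends on the label.

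A reader might also infer that all grade 4 reactions escape. That too goes beyond the text. An actual delay of more than 14 days meets the delay criterion directly, and a mandated stop probably does in substance. What remains for grade 4 is an ambiguity.

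**Conclusion.** The point holds in a limited form. As written, a fatal drug-related event classed as hypersensitivity in Cycle 1 is not a DLT under any criterion, so 1/3 can become 0/3 and 2/6 can become 1/6. Both change the action that the rule prescribes. For grade 4 the plan is unclear rather than plainly wrong.

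The size is small on average: under the assumed rates, one cohort's stop probability differs by about 1 to 3 percentage points. The rate p covers whatever escapes the count, which is certain only for fatal events. The documents give no reaction rate, so no probability is offered that the case arises somewhere in the escalation.

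It would be too strong to infer that the trial could escalate past a death unnoticed. The gap is in the pre-specified count, and safety oversight remains in place. The point is still worth fixing, because the definition of a primary endpoint should not need an override to count a drug-related death.

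**What to change.** Reword the catch-all bullet in Protocol 8.5 and the synopsis to: *≥ Grade 3 (excluding fatigue and grade 3 hypersensitivity reactions); any grade 4 or 5 hypersensitivity reaction is a DLT.* Leave the fatigue and grade 3 hypersensitivity exemptions unchanged.

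The cost is one bullet in two places, through a protocol amendment, with no new data or tables. Any Cycle 1 grade 4 or 5 hypersensitivity reaction already recorded must be re-adjudicated through the existing sponsor/DMC field in SAP 10.1. The population decision taken at that DMC meeting, which SAP 8.2 carries into the final analysis, must be revisited. If escalation is already complete, this re-adjudication is most of the benefit.

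The statistical price is that a rare reaction that may not be dose-related would count towards the MTD. The rewording does not define hypersensitivity, nor settle whether a mandated stop after a grade 3 reaction is a delay.
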